14. STATISTICAL CONSIDERATIONS

This sequential biomarker driven screening design is designed to identify promising treatments worthy of additional study.

Co Primary Endpoint

The primary endpoints for this trial is safety and tolerability defined as the number of DLTs and volumetric response as defined in section 10.1.

Secondary Endpoints:

Secondary endpoints include disease response according to RECIST 1.1, pathologic response, local failure rate, regional failure rate, local and regional progression free survival, disease-free survival, and overall survival. All are defined in Section 10.1.

Sample Size and Study Duration:

Because the use of nivolumab with or without ipilimumab is relatively novel in this setting, we will complete a safety run-in prior in each cohort prior to enrolling additional patients. If a single patient in either cohort is permanently unable to undergo surgery as a result of investigational treatment, enrollment to that cohort will close other DLTs are defined in Section 5.4. If this occurs in the nivolumab cohort then the study will close. The safety run in will begin and complete for nivolumab cohort before enrollment begins on the safety-run in ipilimumab cohort. Once both safety run-ins are complete, patients will be randomized to one of the two cohorts. If at any point during the study only one cohort is open for enrollment, all patients will be assigned to that cohort.

The safety run in for each cohort will follow a typical 3+3 design in each cohort. Initially 3 patients will be entered. If 0 out of 3 patients experiences dose-limiting toxicity (DLT), the safety run in will end and the study will proceed. If exactly 1 out of 3 patients has a DLT, an additional 3 patients will be entered in the safety run in. If none of the next 3 patients experiences a DLT, the study will proceed. If at any time 2 (or more) patients experience DLT, the study will terminate. Either arm will be considered promising if the safety run in is successfully completed.

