Additionally, either arm (nivolumab or nivolumab combined with ipilimumab) will be considered promising and worthy of further evaluation if there is strong evidence that the response rate in either arm evaluated independently may be at least 15% (number of patients with volumetric response versus total number of patients treated in that arm). Response rates will also be correlated with RECIST and pathologic response and changes in lymphocyte infiltration of primary tumor deposits.

The decision rule will be based on the lower bound of the one-sided, 90% exact binomial confidence interval. With this criteria, the treatment will be considered promising if 6 or more of the 20 patients (including patients in the safety-run in) in either arm demonstrate a response. This

would correspond to a lower confidence bound that is at least 15%. If none of the first 10 patients in either arm have a response, then enrollment will stop. Analyses of response rates will be presented by treatment arm within disease accompanied by exact 80% confidence intervals. For a sample of size 20 per arm, each confidence interval will be no wider than 0.32. We will also estimate an aggregated response rate for each treatment modality and present with 80% exact confidence intervals.

Correlative studies will be largely exploratory in nature. We will attempt to correlate PD-L1 expression, mutational burden, T-cell infiltration and initial tumor burden with volumetric, RECIST and pathologic response. We will measure changes in radiologic and pathologic parameters and IHC staining over the course of therapy and correlate these with response and changes in immune markers present in the peripheral circulation.

The accrual goal for this study is 40 patients. We anticipate enrolling approximately 2 patients per month. Therefore, we expect to completely accrue to this study in approximately 20 months. The results should be made public within 24 months of reaching the end of the study. The end of the study is the time point at which the last data items are reported or after the outcome data are sufficiently mature for analysis, as defined above.

Analysis of Endpoints:

The primary endpoint is volumetric response, which will be assessed among all patients who initiate protocol therapy. Response will be assessed as defined in section 10.1. The response rate will be reported with 90% exact confidence intervals.

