All patients who initiate protocol therapy will also be evaluated for response using RECIST v1.1, pathologic response at the time of surgery, safety and tolerability, local failure rate, regional failure rate, local and regional progression free-survival and overall survival. PFS and OS will be analyzed using Kaplan–Meier product-limit estimates and will be plotted using Kaplan-Meier plots. PFS is defined as the time from study randomization to disease progression according RECIST 1.1, medical judgment or death due to any cause, whichever occurred first. Patients alive without disease progression are censored at the date of last disease evaluation. The hazard ratio for each time-to-event endpoint will be estimated with 95% confidence intervals derived from the Cox proportional hazard model, but no hypothesis testing will be conducted. Other definitions are provided in section 10.1.

All patients will be evaluable for toxicity from the time of their first treatment with any study agent. Toxicity will be graded according to NCI CTCAE, Version 4.0. Toxicities will be summarized by maximum grade and by treatment arm. Incidence rate of each toxicity will be reported with 95% exact CI.

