3.7 DF/HCC Multi-Center Protocol Registration Policy

3.7.1 Participant Registration and Randomization

To register a participant, the following documents should be completed by the research nurse or data manager and e-mailed to the Coordinating Center or study coordinator:

- Copy of screening test results, including imaging and pathology results
- Signed participant consent form
- HIPAA authorization form
- Eligibility checklist
- Clinic note, covering screening requirements and baseline AEs

The research nurse or data manager at the participating site will send the registration packet via email to the project manager at DFCI CTO. To complete the registration process, the coordinator will follow DF/HCC Standard Operating Procedure for Human Subject Research Titled *Subject Protocol Registration* (SOP #: REGIST-101A) and register the participant on the protocol. The coordinator will e-mail the participant study number and treatment assignment to the participating site.

Subjects will be randomized by HCRN DF/HCC Office of Data Quality (ODQ) in a 1:1 ratio to either Cohort 1 or Cohort 2. Following registration and randomization, subjects may begin protocol treatment. Issues that would cause treatment delays should be discussed with the sponsor-investigator.

Randomization can only occur during ODQ's normal business hours, Monday through Friday from 8:00 AM to 5:00 PM Eastern Time.

Treatment may not begin without confirmation from the Coordinating Center that the participant has been registered.

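### The planned Cox hazard ratios include patients who were never randomised (at least 6 of 40 if both arms fill), and those patients have no start date for PFS

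*Combined protocol and SAP*

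**What the plan says.** All of the following is in Section 14 of the combined protocol and SAP unless stated otherwise.

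- **Allocation.** Each cohort has its own 3+3 run-in, and the nivolumab run-in finishes before the combination run-in opens. Then: "Once both safety run-ins are complete, patients will be randomized to one of the two cohorts". There is a further exception: "If at any point during the study only one cohort is open for enrollment, all patients will be assigned to that cohort". Appendix D, Section 3.7.1, gives the ratio without mentioning either exception: "Subjects will be randomized by HCRN DF/HCC Office of Data Quality (ODQ) in a 1:1 ratio to either Cohort 1 or Cohort 2". No allocation method, block size or stratification is given.
- **Size.** "The accrual goal for this study is 40 patients". Run-in patients are part of each arm's 20, because the response rule counts "6 or more of the 20 patients (including patients in the safety-run in) in either arm demonstrate a response".
- **Analysis.** Time-to-event endpoints are evaluated in every patient who starts treatment, and "The hazard ratio for each time-to-event endpoint will be estimated with 95% confidence intervals derived from the Cox proportional hazard model". The same sentence adds that no hypothesis will be tested. No contrast, covariate or stratum is named.
- **Time origins.** Section 14 times PFS from randomisation. Sections 10.1.7 and 10.1.8 time local and regional progression-free survival from enrolment. Section 10.1.9 times disease-free survival from first study treatment.

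**The concern.** Section 1.1 describes the trial as randomised, and these hazard ratios are its only planned formal between-arm estimates. A reader of the results will take them as randomised evidence. Some of the patients in them were placed in a cohort known before enrolment, and the run-in patients were placed in calendar order, nivolumab first. Nothing restricts the Cox model to randomised patients, stratifies or adjusts it for enrolment phase, or labels the result. If patients chosen for a known regimen differ in prognosis from those randomised later, that difference enters the hazard ratio as if it were a treatment effect. The 95% interval does not allow for it.

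There is also a problem of definition. A run-in or fill-in patient has no randomisation date, so PFS as written cannot be computed for patients whom the same section says will be analysed.

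**Working it through.** **The plan's own figures.** "The decision rule will be based on the lower bound of the one-sided, 90% exact binomial confidence interval", to be compared with 15%. The exact lower bound for 6/20 is 16.6% and for 5/20 is 12.7%, so 6 is the smallest passing count, as stated. The widest exact 80% interval at n = 20 is 0.324, which agrees to two decimals with "each confidence interval will be no wider than 0.32". These figures treat each arm alone and do not depend on how patients were allocated. The plan gives no event count or precision for the hazard ratios.

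**Run-in patients.** Each run-in that passes has size a or b equal to 3 or 6, and the two expand independently:

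- 3 + 3 = 6 (15.0% of 40)
- 3 + 6 or 6 + 3 = 9 (22.5%)
- 6 + 6 = 12 (30.0%)

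For a DLT probability p per patient, assumed equal in both cohorts, a run-in passes at size 3 with probability A = (1−p)³ and at size 6 with probability B = 3p(1−p)²(1−p)³. Given that both pass, P(6) = [A/(A+B)]², P(9) = 2AB/(A+B)² and P(12) = [B/(A+B)]². For p from 5% to 30%, P(6) runs from 0.78 to 0.48, P(9) from 0.21 to 0.42 and P(12) from 0.01 to 0.09.

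**Fill-in patients, balanced allocation.** Assume tightly balanced 1:1 allocation with both cohorts filling to 20. The number randomised is 2 × min(20−a, 20−b), and the rest of the 40 are not randomised.

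| Run-ins | Run-in patients | Fill-in | Randomised | Not randomised |
|---|---|---|---|---|
| 3 + 3 | 6 | 0 | 34 | 6 |
| 3 + 6 or 6 + 3 | 9 | 3 | 28 | 12 |
| 6 + 6 | 12 | 0 | 28 | 12 |

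**Fill-in patients, simple allocation.** The documents give only the ratio, so this is the other plausible assumption. In 50,000 simulated trials per case, with each arm capped at 20, mean fill-in was 4.6, 5.0 and 4.2 patients for run-in totals of 6, 9 and 12. The mean non-randomised totals are therefore about 10.6, 14.0 and 16.2 of 40.

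**Early closure.** Section 14 stops enrolment when none of the first 10 patients in an arm respond. Suppose this closes one arm only, after run-ins of 3 + 3 and 7 + 7 randomised patients, and the other arm continues from 10 to 20. The trial then has 30 patients, of whom 14 were randomised and 6 + 10 = 16 were not. The chance of 0/10 is 0.85¹⁰ = 0.20 at a 15% response rate and 0.70¹⁰ = 0.03 at 30%.

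**Cost in precision.** If events are proportional to patients, the interval on the log scale widens by √(40/34) = 1.08 with 34 randomised and by √(40/28) = 1.20 with 28.

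**PFS origin.** Set side by side, the analysis set is everyone treated, and the PFS clock starts at an event that 6 or more of them never had. First study treatment, already used for disease-free survival, exists for every treated patient.

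**The case against.** The strongest case against the point is that nothing rests on these hazard ratios. Section 14 calls the trial a screening design and judges each arm independently. The survival objective in Section 1.3 is to estimate one-year rates, the endpoints are secondary, and no test is planned. All of that stands, and it limits the consequence. It does not make an unlabelled, partly non-randomised hazard ratio a randomised one.

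A second argument is that leaving patients out may make the estimate worse. In simulations with 20 per arm, a true hazard ratio of 1, three years of follow-up and assumed annual hazards of 0.15, 0.3 and 0.6, the hazard of pre-assigned combination patients was multiplied by 0.5 or 0.67. The all-treated estimate had the lower mean squared error in all 12 scenarios. With 6 pre-assigned per arm, a multiplier of 0.5 and a hazard of 0.3, the figures were 0.228 for all-treated and 0.267 for randomised-only. With about 15 events (assumed), the 95% half-width on the log scale is 1.96 × √(4/15) = 1.0, well above the simulated bias of roughly 0.05 to 0.21. This is a fair reason to report both estimates. It concerns precision and does not settle whether the all-treated figure may stand as a randomised comparison.

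Third, treatment arm as the contrast is inferred. That is correct, and the sponsor should name it.

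Fourth, calendar drift may be small. At the planned 2 patients a month, 6 to 12 run-in patients take 3 to 6 months, pauses aside, and nothing in the documents suggests a change in staging or adjuvant care. That also stands.

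**Conclusion.** The point holds as a matter of definition and labelling for secondary, descriptive estimates. Under the plan as written, at least 6 of 40 patients in the Cox model were not randomised if both arms fill. Balanced allocation gives 6 or 12. Simple allocation gives about 11 to 16 on average, and early closure of a cohort can raise the share further. PFS has no start date for any of these patients.

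Three stronger readings are tempting, and the documents support none of them:

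- **That the hazard ratio is biased by a known amount in favour of the combination.** The hazard multipliers of 0.5 and 0.67 above are assumptions without a source. The opposite direction is equally possible. Both run-ins use the same eligibility criteria, so selection common to both would largely cancel when they are equal in size. Size and direction are unknown.
- **That the non-randomised number is fixed at 6 or 12.** This requires balanced allocation and both cohorts filling to 20, and the plan states no allocation method.
- **That the trial's conclusions are compromised.** The 6/20 rule treats each arm separately and may properly include run-in patients.

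**What to change.** In Section 14:

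1. Name treatment arm as the contrast for the hazard ratios.
2. Estimate each hazard ratio in patients who went through the 1:1 randomisation, by assigned arm (at most 34 or 28 patients under balanced allocation).
3. Report any all-treated hazard ratio alongside it, labelled descriptive and non-randomised.
4. Keep all treated patients in the per-arm Kaplan-Meier curves and in the 6/20 rule.
5. Define a PFS origin that exists for every patient plotted, for example first study treatment, as Section 10.1.9 does for disease-free survival.

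Appendix D, Section 3.7.1, should mention the run-in and single-open-cohort exceptions so that the two places agree.

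This takes a few sentences. Sample size, data collection and the go/no-go rule do not change. The interval on the randomised-only hazard ratio is about 8% to 20% wider on the log scale under balanced allocation, and wider still if there is more fill-in. The change should be made before outcomes are seen.

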15. PUBLICATION PLAN

We expect this study to produce at least 1 abstract that will be presented at a national meeting, as well as a publication reporting the final results of the study. We will plan on submitting the study results approximately 2 years after the accrual is complete, allowing additional time for toxicity.

Appendix A: Performance Status Criteria

ECOG Performance Status Scale		Karnofsky Performance Scale	
Grade	Description	Percent	Description
0	Normal activity. Fully active, able to carry on all pre-disease performance without restriction.	100	Normal, no complaints, no evidence of disease.
		90	Able to carry on normal activity; minor signs or symptoms of disease.
1	Symptoms, but ambulatory. Restricted in physically strenuous activity, but ambulatory and able to carry out work of a light or sedentary nature (e.g., light housework, office work).	80	Normal activity with effort; some signs or symptoms of disease.
		70	Cares for self, unable to carry on normal activity or to do active work.
2	In bed < 50% of the time. Ambulatory and capable of all self-care, but unable to carry out any work activities. Up and about more than 50% of waking hours.	60	Requires occasional assistance, but is able to care for most of his/her needs.
		50	Requires considerable assistance and frequent medical care.
3	In bed >50% of the time. Capable of only limited self-care, confined to bed or chair more than 50% of waking hours.	40	Disabled, requires special care and assistance.
		30	Severely disabled, hospitalization indicated. Death not imminent.
4	100% bedridden. Completely disabled. Cannot carry on any self-care. Totally confined to bed or chair.	20	Very sick, hospitalization indicated. Death not imminent.
		10	Moribund, fatal processes progressing rapidly.
5	Dead.	0	Dead.

CONFIDENTIAL

This document is confidential. Do not disclose or use except as authorized.

Appendix B: Methods of Contraception

At a minimum, subjects must agree to use one highly effective OR one less effective method of contraception as listed below:

Highly Effective Methods Of Contraception

Highly effective methods of contraception have a failure rate of < 1% when used consistently and correctly. WOCBP and female partners of male subjects, who are WOCBP, are expected to use one of the highly effective methods of contraception listed below. Male subjects must inform their female partners who are WOCBP of the contraceptive requirements of the protocol and are expected to adhere to using contraception with their partner. Contraception methods are as follows:

1. Progestogen only hormonal contraception associated with inhibition of ovulation.
2. Hormonal methods of contraception including oral contraceptive pills containing combined estrogen + progesterone, vaginal ring, injectables, implants and intrauterine devices (IUDs) such as Mirena®
3. Nonhormonal IUDs, such as ParaGard®
4. Bilateral tubal occlusion
5. Vasectomised partner with documented azoospermia 90 days after procedure

Vasectomised partner is a highly effective birth control method provided that partner is the sole sexual partner of the WOCBP trial participant and that the vasectomised partner has received medical assessment of the surgical success.

6. Intrauterine hormone-releasing system (IUS).
7. Complete abstinence

Complete abstinence is defined as the complete avoidance of heterosexual intercourse.

Complete abstinence is an acceptable form of contraception for all study drugs and must be used throughout the duration of the study treatment (plus 5 half-lives of the investigational drug plus 30 days).

It is not necessary to use any other method of contraception when complete abstinence is elected.

Subjects who choose complete abstinence must continue to have pregnancy tests

Acceptable alternate methods of highly effective contraception must be discussed in the event that the subject chooses to forego complete abstinence.

The reliability of sexual abstinence needs to be evaluated in relation to the duration of the clinical trial and the preferred and usual lifestyle of the subject.

Less Effective Methods Of Contraception

1. Diaphragm with spermicide
2. Cervical cap with spermicide
3. Vaginal sponge with spermicide
4. Male or female condom with or without spermicide*
5. Progestogen-only oral hormonal contraception, where inhibition of ovulation is not the primary mode of action

* A male and a female condom must not be used together.

Unacceptable Methods Of Contraception

1. Periodic abstinence (calendar, symptothermal, post-ovulation methods)
2. Withdrawal (coitus interruptus)
3. Spermicide only

4. Lactation amenorrhea method (LAM)

Appendix C: Management Algorithms

- These general guidelines constitute guidance to the Investigator. The guidance applies to all immuno-oncology (I-O) agents and regimens.
- A general principle is that differential diagnoses should be diligently evaluated according to standard medical practice. Non-inflammatory etiologies should be considered and appropriately treated.
- Corticosteroids are a primary therapy for immuno-oncology drug-related adverse events. The oral equivalent of the recommended IV doses may be considered for ambulatory patients with low-grade toxicity. The lower bioavailability of oral corticosteroids should be taken into account when switching to the equivalent dose of oral corticosteroids.
- Consultation with a medical or surgical specialist, especially prior to an invasive diagnostic or therapeutic procedure, is recommended.
- The frequency and severity of the related adverse events covered by these algorithms will depend on the immuno-oncology agent or regimen being used

Investigators should refer to the most current version of the nivolumab or ipilimumab IB for current recommendations for management of a specific Adverse Event of interest.

1. INTRODUCTION

The Dana-Farber/Harvard Cancer Center Multi-Center Data and Safety Monitoring Plan (DF/HCC DSMP) outlines the procedures for conducting a DF/HCC Multi-Center research protocol. The DF/HCC DSMP should serve as a reference for any sites external to DF/HCC that will be participating in the research protocol.

1.1 Purpose

To establish standards that will ensure that a Dana-Farber/Harvard Cancer Center Multi-Center protocol will comply with Federal Regulations, Health Insurance Portability and Accountability Act (HIPAA) requirements and applicable DF/HCC Standard Operating Procedures.

1.2 Multi-Center Data and Safety Monitoring Plan Definitions

DF/HCC Multi-Center Protocol: A research protocol in which one or more outside institutions are collaborating with Dana-Farber/Harvard Cancer Center where a DF/HCC investigator is the sponsor. DF/HCC includes Dana-Farber/Partners Cancer Care (DF/PCC) Network Clinical Trial Affiliates.

Lead Institution: One of the Dana-Farber/Harvard Cancer Center consortium members (Dana-Farber Cancer Institute (DFCI), Massachusetts General Hospital (MGH), Beth Israel Deaconess Medical Center (BIDMC), Boston Children's Hospital (BCH), Brigham and Women's Hospital (BWH)) responsible for the coordination, development, submission, and approval of a protocol as well as its subsequent amendments per the DFCI IRB and applicable regulatory guidelines (CTEP, Food and Drug Administration (FDA), Office of Biotechnology Activities (OBA) etc.). The Lead Institution is typically the home of the DF/HCC Sponsor.

DF/HCC Sponsor: The person sponsoring the submitted Multi-Center protocol. Within DF/HCC, this person is the Overall Principal Investigator who takes responsibility for initiation, management and conduct of the protocol at all research locations. In applicable protocols, the DF/HCC Sponsor will serve as the single liaison with any regulatory agencies (i.e. FDA, OHRP, etc.). The DF/HCC Sponsor has ultimate authority over the protocol and is responsible for the conduct of the study at DF/HCC and all Participating Institutions. In most cases the DF/HCC Sponsor is the same person as the DF/HCC Overall Principal Investigator; however, both roles can be filled by two different people.

Participating Institution: An institution that is outside the DF/HCC and DF/PCC consortium that is collaborating with DF/HCC on a protocol where the sponsor is a DF/HCC Investigator. The Participating Institution acknowledges the DF/HCC Sponsor as having the ultimate authority and responsibility for the overall conduct of the study.

Coordinating Center: The entity (i.e. Lead Institution, Medical Monitor, Contract Research Organization (CRO), etc) that provides administrative support to the DF/HCC Sponsor in order that he/she may fulfill the responsibilities outlined in the protocol document and DSMP, and as specified in applicable regulatory guidelines (i.e.

CTEP Multi-Center Guidelines). In general, the Lead Institution is the Coordinating Center for the DF/HCC Multi-Center Protocol. Should the DF/HCC Sponsor decide to use a CRO, the CRO will be deemed the Coordinating Center.

DF/HCC Office of Data Quality (ODQ): A group within DF/HCC responsible ensuring high-quality standards are used for data collection and the ongoing management of clinical trials, auditing, and data and safety monitoring. ODQ also coordinates quality assurance efforts related to multi-center clinical research.

DF/HCC Clinical Trials Research Informatics Office (CTRIO): A group within DF/HCC responsible for providing a comprehensive data management platform for managing clinical trial data.

